55-74). There were 297 individuals who were reachable and 54 of these were eligible for LCS according to the USPSTF criteria. We were able to contact a higher proportion of current smokers (47%) than former smokers (30%). Eligibility was higher in current smokers (28%) versus former smokers (11%). Also, of the 54 total eligible, 28 enrolled. Despite these small numbers, we were able to show the DCP participation was associated with LDCT completion at 90 days ($p=0.03$).

Study Design We propose a 1 year project including a **6 month intervention** period. This study will be a cohort with comparison to usual care in other practices in the same health system using propensity-matching methodology. **Study population/eligibility** Inclusion/exclusion criteria will be based on the USPSTF and CMS lung cancer screening guidelines: age 55- 80, with a 30 pack year smoking history, no symptoms consistent with cancer, and no CT scan of the lungs within the last year. Physicians will be given the chance to eliminate participants based on limited life expectancy or prohibitive comorbid conditions. Case finding in our prior work was difficult and recruiting active smokers has a higher yield. Prior work indicated that this pool yielded a higher proportion of truly eligible, reachable individuals. Plus, we want to test the feasibility of a more intense smoking cessation intervention. To address recruitment barriers, we will work with practices and PCPs to promote as a study “conducted with the PCP,” including the physician name or practice name when possible on recruitment materials e.g. written letters and email cosigned by their PCP. To address case finding barriers, we will allow patients to easily opt out of future contact via mail, email or phone. We will work with our advisory panel to explore other methods to enhance recruitment and case-finding such as using the secure EMR portal to screen for LCS eligibility and/or updating smoking history. Finally, we have added \$50 patient incentives per patient for participation.

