Intervention The DCP is an online software application that supports an interactive session that focuses on patient education and preference clarification. Patients will be contacted by phone or other methods to provide information about the study, be invited to participate, consented, and then scheduled for decision counseling. Neither the DCP tool nor this process is directive; the DCP session does not push the patient to screen but, rather, clarifies the patient's current preference (screen or not) and identifies key reasons for that preference. In the session, the decision counselor and patient will review the options, (to screen or not to screen for lung cancer) using publicly available patient education materials (Appendices 1 & 2) (8, 9). Then, the decision counselor will guide the patient through 5 steps: 1) identify factors most likely to influence the decision to screen 2) assign importance (decision weight) to the factors 3) compare the relative weight of the most important factors 4) generate a decision score, and 5) generate a personal summary form which can be made available in the EMR for physician review with the patient. Next steps will be tailored to each practice, and can include referral to PCP for further discussion and/or referral to the Lung Health Screening Program (LHSP). The decision counselor will be trained as a smoking cessation coach and as a “mini-expert” in system and community resources for smoking cessation.

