Data Acquisition Following approval by the CCHS Institutional Review board, lists of potentially eligible individuals from participating and non-participating practices will be obtained from EMR data. These lists will be automatically entered into a REDCap® for CONSORT tracking. Lists will be organized according to PCP whom will be given 7 working days to review lists and eliminate any patient they feel would not be appropriate for this study. Remaining potentially eligible patients will receive a letter, cosigned by their personal physician which introduces the study and offers the opportunity to easily opt out of further contact. After an opt-out period of 7 working days, patients will be contacted, screened for eligibility and invited to participate. After formal consent, we will collect demographics, socioeconomic variables and smoking history. Baseline data will be collected regarding knowledge, preference and decisional conflict related to lung cancer screening. Standard patient education materials will be sent to patients. The DCP session will be conducted within 30 days of enrollment. A follow up telephone call will occur within 30 days of DCP completion, and will include items to assess patient perception of the process, knowledge about lung cancer screening and decisional conflict (Appendix 3) related to lung cancer screening (10). At 60 days after the decision counseling session, patient charts/electronic medical record data will be audited for the primary outcome, LDCT scan report. Prior work showed the average time from DCP to LDCT was ≤ 60 days. Intermediate (process) outcomes in EMR include lung cancer screening discussion, referral/order for LDCT, or referral to the CCHS LHSP. Eligible patients in the usual care group (in the non-participating clinics) will be identified electronically as stated above and LDCT screening assessed in a 60 day study period from their most recent office visit. Information available in EMR for all patients including controls and individuals who are “unreachable” comprises gender, age, race, ethnicity, insurance status, marital status, smoking status, comorbidities, such as COPD, Heart disease, diabetes, hypertension and zip code (surrogate for socioeconomic status). Information collected from individuals who are reached but ineligible will include all of the above plus smoking status, pack years, and reason for ineligibility. Information collected from individuals who decline participation will include all of the above plus reason for declining participation.

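### The controls' 60-day LDCT window is anchored backward on the most recent office visit, with no eligibility date or full-capture rule, so a later visit can drop a scan from the primary outcome

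*Combined protocol and SAP*

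**What the plan says.** **DCP group.** Data Acquisition states: "At 60 days after the decision counseling session, patient charts/electronic medical record data will be audited for the primary outcome, LDCT scan report". Eligibility is settled earlier, when "patients will be contacted, screened for eligibility and invited to participate", and "The DCP session will be conducted within 30 days of enrollment". Time zero is thus a dated event that follows eligibility, and the audit waits until the 60 days are over.

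**Controls.** The same section says that "lists of potentially eligible individuals from participating and non-participating practices will be obtained from EMR data", that usual-care patients "will be identified electronically as stated above", and that they have "LDCT screening assessed in a 60 day study period from their most recent office visit".

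**Eligibility.** Study population/eligibility requires "no CT scan of the lungs within the last year". For controls, the date from which that year is counted is not given.

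**Analysis.** Aim 1 matches 1-to-1 on a propensity score built from patient-level EMR variables and compares LDCT completion within 60 days by an unadjusted chi-square. No index or calendar date enters the matching, and control visits are not tied to the six-month intervention period.

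**The concern.** Which visit is the most recent is known only after all later visits have been seen, so events after a scan can decide where the window starts. This opens three routes to a distorted control rate:

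- **Reset.** A control has a visit, is scanned within 60 days, and returns for the result. The return visit is now the most recent one, and the scan lies before time zero. The control is scored as unscreened, or is excluded if the no-CT year is counted back from the new time zero.
- **Eligibility judged after the visit.** If the no-CT year is counted back from a list pull that follows the visit, controls scanned between visit and pull are removed. Those removed are the very patients with the outcome.
- **Cut follow-up.** If the visit is read from the final extraction and no wait is required, a late visit leaves fewer than 60 days of data.

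DCP patients face none of these. The Aim 1 difference would then mix an artefact of time zero with the effect of DCP. Balance on age, insurance or comorbidity does not remove it, because it arises from dates and not from patient characteristics.

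**Working it through.** **1. The plan's own figure.** The power calculation takes 15% (usual care) against 45% (DCP) with 40 per group. With a two-sided 5% level (assumed; none is stated) and pooled variance:

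- SE under the null = sqrt(2 × 0.30 × 0.70 / 40) = 0.1025
- SE under the alternative = sqrt((0.15 × 0.85 + 0.45 × 0.55) / 40) = 0.0968
- z = (0.30 − 1.96 × 0.1025) / 0.0968 = 1.02, so power is 84.7%

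The stated 85% reproduces. The 15% carries no time period, so it does not show which reading of the control window was meant.

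**2. Reset, by arithmetic.** Suppose a share q of scanned controls return and reset time zero (q is assumed). The observed rate is 0.15 × (1 − q) if they count as unscreened, or 0.15 × (1 − q) / (1 − 0.15q) if they are excluded.

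| q | Counted as unscreened | Excluded |
|---|---|---|
| 10% | 13.5% | 13.7% |
| 25% | 11.3% | 11.7% |
| 50% | 7.5% | 8.1% |

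**3. Cut follow-up, by arithmetic.** With visits at random at r per year (assumed), the share of controls whose last visit falls under 60 days before extraction is 1 − exp(−60r/365): 0.28 at r = 2 and 0.48 at r = 4. If half of their scans are captured, 15% becomes 0.15 × (1 − 0.5 × 0.28) = 12.9%, or 0.15 × (1 − 0.5 × 0.48) = 11.4%.

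**4. All routes together, by simulation.** There were 60,000 controls per setting, with random (Poisson) visits, no new order within 12 months after a scan, list pull at day 0, intervention over days 0-180 and extraction at day 240. All rates are assumed: 2 or 4 visits a year; 2%, 5% or 15% of visits leading to an LDCT 3-60 days later; 0 or 60% of scans followed by a visit within 30 days. These imply 3.8-7.5%, 9.1-16.6% and 22.5-36.4% screened per year. For comparison, Specific Aims cites 3.9% nationally for 2015.

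Control rates (%) are listed in the order 2 visits/yr without scan-triggered visits, 2/yr with 60%, 4/yr without, 4/yr with 60%.

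| Reading of the rule | 2% per visit | 5% per visit | 15% per visit |
|---|---|---|---|
| A. Last visit before extraction, eligible at visit, full 60 days | 2.3/1.3/2.8/1.9 | 6.0/3.4/7.0/4.5 | 17.2/10.1/20.1/13.6 |
| B. As A, cut at extraction | 2.0/0.9/2.0/1.0 | 5.1/2.4/5.1/2.5 | 14.4/7.1/14.4/7.5 |
| C. As B, eligible at list pull | 1.5/0.7/1.8/0.9 | 3.9/1.8/4.4/2.1 | 10.0/4.6/10.9/5.2 |
| D. Last visit before list pull, eligible at list pull | 0.6/0.5/0.8/0.8 | 1.5/1.2/1.9/2.0 | 4.4/3.4/5.8/5.4 |
| E. As D, eligible at visit | 2.5/1.4/2.8/1.8 | 5.8/3.2/6.8/4.4 | 17.2/10.1/19.7/13.1 |
| Highest minus lowest | 1.9/0.9/2.0/1.1 | 4.5/2.2/5.1/2.5 | 12.8/6.7/14.3/8.4 |

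A reading with the no-CT year counted back from final extraction is left out.

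What drives the differences:

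- A and E differ only in the date from which the last visit is read. They lie 0 to 0.5 points apart, so that date alone hardly matters.
- The spread comes from the eligibility date and from cut follow-up. Reading D is lowest in 11 of 12 settings.
- Scan-triggered visits alone lower reading A by 32% to 43% of its value: for example 6.0 to 3.4, 17.2 to 10.1, and 20.1 to 13.6.

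**5. Against a neutral date.** If controls are indexed at a session date unrelated to their visits, the rates are 0.6/0.6/1.3/1.3, 1.7/1.6/3.2/3.2 and 4.7/4.9/9.3/9.1. Readings A to E minus these values run from −0.5 to +1.9, −1.3 to +4.3 and −3.9 to +12.5 points. An index at the first visit in the intervention period gives +1.5 to +1.8, +3.6 to +4.4 and +10.3 to +12.4. In all six settings with scan-triggered visits, the first-visit index lies further from the neutral date than any of A to E.

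**The case against.** The strongest case against is that this is missing detail in a pilot. A 60-day period naturally means 60 full days, which sets aside readings B and C. Reading D would largely erase the outcome it is meant to measure, so nobody would intend it. With those gone, A and E agree to within half a point. At the 2% and 5% settings even the full spread is 1-5 points against a target of 20-30, and the larger figures need 15% of visits to lead to a scan. Usual care has no counseling session, so some difference of anchor is inevitable.

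Much of this stands. The missing reference date is not in itself the problem, the widest spread does rest on the less natural readings, and no visit or order rate is in the documents.

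Two things survive. The reset follows from the rule as written: under A and E, with full follow-up and eligibility at the visit, scan-triggered visits still remove roughly a third or more of the control rate. And the plan leaves the eligibility date and full capture to whoever writes the query. Pilot status does not excuse this, since Aim 1 has a hypothesis, a power calculation and a test, and the work is meant to prepare a randomized trial. The different anchor can also be avoided, because a control can be given a date without having had a session.

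**Conclusion.** The point holds as a defect in how the control outcome is defined, to be repaired before extraction. That the rule looks backward and that the eligibility date and capture requirement are absent can be read directly from the text. The size is illustrative only and depends on the assumed visit, order and return-visit rates.

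Three stronger conclusions are tempting but not supported:

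- **That the rule favours DCP.** Reset, late eligibility and cut follow-up lower the control rate. But a control window opens at a visit, where a scan can be ordered, whereas after a DCP session the next steps "can include referral to PCP for further discussion and/or referral to the Lung Health Screening Program (LHSP". That difference can raise the control rate. In the illustration the net sign depends on the reading, and is more often against DCP.
- **That the control rate is zero by construction.** This needs the no-CT year to be counted from the list pull and the control windows to have closed within that year. The plan states neither.
- **That 7-14 points is the expected error.** This needs 15% of visits to lead to a scan, which fits only if the planning rate of 15% is a 60-day post-visit rate.

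**What to change.** Before extraction, replace the most-recent-visit rule with a common index:

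- Give each control the matched DCP patient's session date as time zero.
- Match only among controls who meet the eligibility criteria, including the 12-month no-CT look-back, as of that DCP patient's enrollment date, using no later data. This puts eligibility at the same point in both groups and avoids losing controls after matching.
- Count LDCT over a full 60 days from the session date in both groups, and extract no earlier than 60 days after the last session.
- As a sensitivity analysis, index controls at their first qualifying office visit in the six-month intervention period, with eligibility judged at that visit and a full 60 days captured. State that a visit anchor may raise the control rate; for that reason it should not be the primary analysis.

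The cost is a revised EMR query, a date-aware matching step and one paragraph in the analysis plan, with no extra patient contact. Some controls not eligible on the assigned date are unavailable for that match. The wait for extraction is one that the DCP audit already needs. The sensitivity analysis loses controls without a visit in the six months: exp(−180r/365) = 37% at 2 visits a year or 14% at 4 (assumed rates). The primary analysis needs no visit and keeps them.

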
Statistical analysis

Aim 1 Compare low dose CT scan completion in the DCP cohort of current smokers versus usual care propensity-matched controls at 60 days. *Hypothesis: Participation in the DCP will be associated increased participation in LDCT, compared with both eligible enrollees who do not participate and with eligible patients in usual care practices.* Demographic and clinical variables of the intervention and control groups will be compared using T-Test, Wilcoxon-Rank sum test and chi-squares. We will conduct a 1-to-1 propensity score matching to compare the proportion of patients who screen between the groups. We will use a logistic regression model to build propensity scores to match patients in the intervention and control groups. We will model the probability of being in the intervention group using all the patients level variables extracted from the medical records as listed above. Whether they are in a participating practice or not will not be included in the model as an independent variable. The nearest neighborhood method without replacement will be used for matching. We will set the caliper width according to the standard deviation for the propensity score. Each control will be assigned a probability score and matched with a patient in the intervention group. In a second step, we will compare the characteristics of the patients and chosen controls to verify that they are very similar. We will use a simple chi-square to compare the percentage of patients in the control and intervention groups who complete the LDCT scan within 60 days.

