Power calculation based on primary outcome: According to our preliminary study, 45% of those who complete the DCP decided to screen for lung cancer whereas the know rate of screening among patients in usual care is 15%, which makes a difference of 30%. A sample size of 40 patients in each group will achieve 85% power to detect a difference between the group proportions of 30%. The proportion in the intervention group is assumed to be 15% under the null hypothesis and 45% under the alternative hypothesis. To detect a difference of 20%, we will need a sample size of 60 patients in each group to achieve a power of 80%. We expect that 2000 patients will be identified as potentially eligible for the study in the EMR and 1000 will be reachable. Of those 300 (30%) will be confirmed eligible during the phone call and 150 (50%) will accept to participate in the DCP. We will therefore have ample power to detect a difference as small as 20% between our 2 groups.

Aim 2 Compare the characteristics of the patients not recruited in the study to the characteristics of those who accepted to enroll. *Hypothesis: Patients recruited to the study versus those who are not will be different demographically and geographically.* We will use descriptive statistics to examine the characteristics of the patients of the intervention practices who were eligible but could not be reached and of the patients who were reached but refused to be in the study. We will also compare the characteristics of these patients to those of the patients who enrolled in the study. We will use logistic regression models to determine which independent characteristics are associated with agreeing to be in the study.

Aim 3 Test the feasibility of intensive smoking cessation as part of the DCP. *This aim is hypothesis generating.* At 30 days, we will ask patients about participation in smoking cessation, quit attempts and for general comments on their needs and satisfaction with our smoking cessation efforts. We will explore trends associated with these intermediate outcomes related to cessation including engaging in cessation and quit attempts. We will illicit qualitative information from participants about how to make this part of the program useful and patient-centered.

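### Fixed 1-to-1 matching leaves usable usual-care controls aside; allowing up to two or three per DCP patient is a cheap precision gain, and the 60-per-group power figure needs restating

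*Combined protocol and SAP*

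**What the plan says.** In the combined protocol and SAP, Statistical analysis, Aim 1, the ratio is fixed: "We will conduct a 1-to-1 propensity score matching". The algorithm is also given: "The nearest neighborhood method without replacement will be used for matching". The caliper is described only in outline: "We will set the caliper width according to the standard deviation for the propensity score", with no multiple stated. Balance is then checked, and the primary comparison is plain: "We will use a simple chi-square to compare the percentage of patients".

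Under Approach, Data Acquisition, both groups start from the same kind of source: "lists of potentially eligible individuals from participating and non-participating practices will be obtained from EMR data". DCP patients then go through physician review, a letter, an opt-out period, phone contact, consent and a counselling session. Usual-care patients are found electronically, and their screening is assessed over 60 days from their latest office visit.

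The power paragraph takes 45% screening after the DCP and 15% in usual care. It gives 40 per group for 85% power at that 30-point difference. For a 20-point difference it says "we will need a sample size of 60 patients in each group to achieve a power of 80" per cent. It then expects 150 participants and calls the power for 20 points ample; Specific Aims gives a target of 100. No reason is given for the 1:1 ratio, and the number of available controls is not stated.

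**The concern.** The two groups cost very different amounts to assemble. DCP patients are recruited one by one and paid an incentive; controls are existing records in a health system that the plan describes as large. When one group is scarce and the other may be plentiful, a fixed 1:1 ratio without replacement sets aside information that could be used with no further recruitment.

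The sample-size statement makes this more visible. If 60 pairs do not deliver the claimed 80% power, extra controls are one way to recover it. What is at stake is mainly the precision of an estimate meant to support a later randomized trial, plus some protection if fewer DCP patients are matched than planned.

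**Working it through.** **Inputs.** Usual-care rate 15%, DCP rate 45%, 40 and 60 per group, 150 expected participants (all from the power paragraph); target of 100 (Specific Aims). Assumed: two-sided 5% test, since alpha and sidedness are not stated; 35% v 15% for the 20-point case, since only one usual-care rate is given; independent patients; enough in-caliper controls.

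**Formula.** With n DCP patients and k controls each, p̄ = (p₁ + k·p₂)/(1 + k) and

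z = [ |p₁ − p₂| − 1.96·√( p̄(1 − p̄)(1/n + 1/(kn)) ) ] / √( p₁(1 − p₁)/n + p₂(1 − p₂)/(kn) ), power = Φ(z).

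**Step 1: the plan's 30-point figure.** n = 40, k = 1, p̄ = 0.30: z = (0.30 − 1.96 × 0.1025)/0.0968 = 1.02, power 84.7%. This reproduces the stated 85%, so the two-sided convention fits.

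**Step 2: the plan's 20-point figure.** n = 60, k = 1, p̄ = 0.25: z = (0.20 − 1.96 × 0.0791)/0.0769 = 0.586, power 72.1%. Other methods agree: unpooled variance 73.9%, arcsine 73.2%, exact enumeration of the chi-square 73.5%. Reaching 80% needs 73 per group. A one-sided test gives 81.8% at 60, but it would give 91.3% at 40 per group for 30 points, so it does not fit the first figure. No single convention tried with the 15% rate reproduces both.

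**Step 3: more controls at 60 DCP patients, 35% v 15%.**

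| Ratio | Pooled formula | Exact chi-square | Unpooled formula | DCP patients for 80% (pooled) |
|---|---|---|---|---|
| 1:1 | 72.1% | 73.5% | 73.9% | 73 |
| 1:2 | 85.0% | 85.9% | 81.9% | 53 |
| 1:3 | 89.2% | 90.0% | 84.6% | 46 |

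The gain is smaller under the unpooled formula: 81.9 − 73.9 = 8.0 points at 1:2 and 84.6 − 73.9 = 10.7 points at 1:3.

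**Step 4: 1:1 at the planned sizes, 35% v 15%.**
- 100 pairs: z = (0.20 − 1.96 × 0.0612)/0.0596 = 1.34, power 91.0%.
- 150 pairs: z = (0.20 − 1.96 × 0.0500)/0.0486 = 2.10, power 98.2%.

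**Step 5: precision at 100 DCP patients, 45% v 15%.** Half-width = 1.96·√(0.45 × 0.55/100 + 0.15 × 0.85/(100k)).
- k = 1: 1.96·√0.003750 = 12.0 points.
- k = 2: 1.96·√0.003113 = 10.9 points; variance falls by 1 − 0.003113/0.003750 = 17%.
- k = 3: 1.96·√0.002900 = 10.6 points; variance falls by 1 − 0.002900/0.003750 = 23%.

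Most of the gain comes from the second control.

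**The case against.** The strongest reply is that the plan does not need rescuing. Sixty is the number the plan says it requires, not the number it expects to enrol. A reader might infer from Step 2 that the study is underpowered for 20 points and that extra controls would restore the power. The documents do not support that: at 100 or 150 matched pairs, 1:1 gives 91% or 98%. Only about 73 matched DCP patients are needed, which is 73% of the target of 100 and 49% (73/150) of the expected 150. This part of the objection stands.

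A shortfall is possible but not shown. The pilot enrolled 28 from a list of over 900; that yield applied to 2000 records gives at most about 62 (28/900 × 2000). Using the pilot's current-smoker rates instead gives about 136 (2000 × 0.47 × 0.28 × 28/54). Losses to the caliper are not projected.

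A reader might also infer that extra controls cost nothing. The documents say that controls are found electronically; they do not say that eligibility and outcome work is free, or how many controls exist. This stands too.

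Finally, more controls buy precision, not validity. Pack years are not among the EMR items listed for controls, so their eligibility is less certain than that of phone-screened DCP patients. The groups come from different practices, and clustering would shrink the gain. Later matches are less close, and the caliper that should limit this has no stated multiple. These limits are real, but the eligibility problem and the practice difference affect 1:1 matching as well, and the planned balance check would show a loss of match quality.

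**Conclusion.** The point holds as an inexpensive improvement. Fixed 1:1 matching is a standard and defensible choice, but it leaves unused any further in-caliper controls that need no recruitment. Using two or three per DCP patient would cut the variance of the difference by 17% or 23% with 100 DCP patients, a reduction of 1.1 or 1.4 points in the half-width. This rests on an adequate control pool, independent patients and the plan's rates of 45% and 15%.

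For the 20-point difference, the change would lift power from below 80% to 80% or more only if about 53 to 72 DCP patients are matched (1:2), or about 46 to 72 (1:3), by the pooled formula. At planned enrolment it is not needed for that purpose.

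The power statement is a separate error and should be corrected whatever ratio is used: at 15% v 35%, two-sided 5%, 60 per group gives about 72%.

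**What to change.** In Statistical analysis, Aim 1, before any outcome data are seen:

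- Replace the fixed ratio with variable-ratio matching within the same caliper, up to two or three controls per DCP patient, and state the caliper multiple.
- Assign a first match to every DCP patient before any second or third match. Without replacement, a second match could otherwise take another patient's only acceptable control.
- Weight controls within each matched set so that each set counts once, and use standard errors that account for the sets instead of the simple chi-square. With unequal set sizes, an unweighted comparison would over-represent patients who are easy to match.
- Report the size of the control pool. Keep 1:1 if the pool is too small or if the planned balance check worsens with added controls.

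In the power paragraph, state alpha, sidedness and the assumed usual-care rate for the 20-point case. Replace 60 per group with about 73 per group at 1:1, or about 53 DCP patients at 1:2.

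The cost is revised wording, some extra data work on controls and a slightly more complex analysis. The trade-off is somewhat less close second and third matches. The change does not address the uncertain pack-year eligibility of controls or clustering by practice; both need their own handling.

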Community Engagement Our team has established relationships with clinical and administrative leadership as would be necessary to conduct this work in a large health system. In addition, we have engaged local community outreach leaders with special knowledge and emphasis on smoking cessation. [name] is a frequent speaker for physician educational events locally, regionally and nationally. In the first two months of the project, we will convene an advisory team of patients, physicians and administrative leaders to guide and champion this work. The advisory team will provide expertise on improving lung cancer screening generally and provide specific advice regarding: practice selection, data acquisition and exchange, improving recruitment methods, adding smoking cessation and planning for sustainability beyond the pilot funding period.

Sustainability This work would lay the groundwork for an R01 level randomized controlled trial. The Agency for Healthcare Research and Quality (AHRQ) has issued a Special Emphasis Notice (SEN) to inform the research community that AHRQ intends to support research on models of shared decision making (SDM) that are tailored to the needs of low income and racial and ethnic minority patients (11). The Patient Centered Outcomes Research Institute (PCORI) has a strong focus on comparative effectiveness research which helps patients to make informed or shared decisions (12). The use of non-physician team members to extend care beyond the visit and to provide proactive care is likely to be cost-effective in improving population health and is aligned with the strategic vision of CCHS.

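### Aim 1 cannot separate practice-level differences in LDCT use from the DCP effect; a re-indexed pre-launch comparison from the same EMR would show and partly correct them

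*Combined protocol and SAP*

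**What the plan says.** The Study Design paragraph describes a non-randomised cohort with "comparison to usual care in other practices in the same health system using propensity-matching methodology". Under Data Acquisition, the source of controls is explicit: "Eligible patients in the usual care group (in the non-participating clinics) will be identified electronically as stated above". DCP patients are approached by a letter that their own physician co-signs, so they belong to the participating practices.

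Under Statistical analysis, Aim 1, the matching model is patient-level: "We will model the probability of being in the intervention group using all the patients level variables extracted from the medical records". Data Acquisition lists the variables as "gender, age, race, ethnicity, insurance status, marital status, smoking status, comorbidities, such as COPD, Heart disease, diabetes, hypertension and zip code". Practice participation is kept out: "Whether they are in a participating practice or not will not be included in the model". After a check that matched patients resemble each other, the outcome is tested simply: "We will use a simple chi-square to compare the percentage of patients in the control and intervention groups".

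On how practices are chosen, Community Engagement says only that an advisory team will "provide specific advice regarding: practice selection, data acquisition and exchange". No random or matched selection of practices is described. Nor is there a pre-launch LDCT rate, a practice-level covariate, a difference-in-differences estimate or a sensitivity analysis.

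**The concern.** Study group and practice type coincide in the primary comparison. Any difference in LDCT completion that already exists between the two sets of practices, and that patient characteristics do not explain, is added to the DCP contrast. The plan gives reason to take this seriously: its Innovation section ranks physician recommendation among the leading predictors of cancer screening, and no listed covariate measures it. The post-match balance check looks at patient characteristics, so it would not reveal the problem.

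The study is meant to prepare a randomised trial. An estimate inflated by a practice gap would make that trial too small, and a gap the other way could end a useful programme early.

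**Working it through.** **Inputs.** Usual-care rate 15% and DCP rate 45%, with 40 per group for 85% power (power calculation). DCP group size 100 (Specific Aims) or 150 (expected participants in the power calculation). Matching is 1:1. The plan states no significance level; two-sided 5% is assumed. No practice-level rates are given, so those below are assumptions.

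**Step 1: the plan's own figure.** Power = Φ{[|p1 − p0|√n − 1.96√(2p̄(1 − p̄))] / √[p0(1 − p0) + p1(1 − p1)]}. With p0 = 0.15, p1 = 0.45, p̄ = 0.30, n = 40:

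- |p1 − p0|√n = 0.30 × 6.325 = 1.897
- 1.96 × √0.42 = 1.270
- √(0.1275 + 0.2475) = 0.612
- (1.897 − 1.270) / 0.612 = 1.02, so power = 84.7%

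The stated 85% reproduces. The calculation treats the whole 30 points as the DCP effect.

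**Step 2: what the contrast estimates.** Let b1 and b0 be the LDCT rates that comparable patients would have in participating and non-participating practices without the DCP, and let δ be the DCP effect. The expected difference is δ + (b1 − b0). Matching on patient variables shrinks the part of b1 − b0 due to measured patient mix and leaves the part due to practice behaviour.

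**Step 3: rejection rate when δ = 0.** Sum the probability of every pair (x, y), x ~ Bin(n, b0) and y ~ Bin(n, b1), for which 2n(x − y)² / [(x + y)(2n − x − y)] ≥ 3.84.

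| Participating v non-participating (assumed) | n = 100 per group | n = 150 per group |
|---|---|---|
| 15% v 15% | 5% | 5% |
| 20% v 15% | 16% | 21% |
| 25% v 15% | 43% | 59% |
| 4% v 3% | 6% | 7% |
| 5% v 3% | 9% | 14% |

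The low-rate rows are there because the plan's 15% has no stated time window and the Specific Aims give national screening rates of 3.3% and 3.9%. Where there is a gap, a larger sample makes a false signal more likely.

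**Step 4: the opposite direction.** Suppose the DCP adds 20 points, but participating practices start at 5% and controls at 15%. The observed contrast is 25% v 15%. The chance of a significant result falls from 91% (35% v 15%) to 43% at 100 per group, and from 98% to 59% at 150.

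**Step 5: can current patients supply a baseline?** Eligibility requires no lung CT within the last year. Among patients who meet that criterion at launch, LDCT completion in the year before launch is zero or near zero in every practice by construction. A naive look-back would therefore falsely reassure. The pre-period cohort must be assembled as of its own earlier index date.

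**The case against.** Several points on the other side stand.

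- **The omitted indicator is not the mistake.** A reader might infer from the quoted sentence that practice participation should go into the propensity model. It should not: it would separate the groups almost completely and leave no matches.
- **The plan is not without protection.** Controls come from the same health system, and matching on insurance, comorbidities and zip code removes the part of a practice difference that reflects measured patient mix. What survives is the practice-level part.
- **Upward bias is not documented.** A reader might infer that the practices volunteer because they are keen screeners. The documents say only that the advisory team advises on selection. The one-year CT exclusion could even work the other way, because high-ordering practices have already removed screened patients from their eligible pool.
- **The illustration is assumption-based.** A 5-point gap is one-sixth of the planned 30-point difference, and at low base rates the distortion is modest.
- **A within-practice contrast is named.** The Aim 1 hypothesis also mentions eligible enrollees who do not participate. That could help, but no LDCT analysis is specified for it, Aim 2 compares characteristics only, and the contrast carries its own self-selection.
- **This is a pilot with an association hypothesis.** True, but it states a comparative hypothesis, powers it, and is intended to inform a randomised trial.

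None of this supplies a way to see or adjust for a practice-level gap in LDCT use.

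**Conclusion.** The concern holds in a limited form. As designed and analysed, Aim 1 folds any practice-level difference in LDCT use, beyond measured patient mix, into the DCP contrast. The bias equals the residual gap in percentage points, whatever its sign. On the assumed gaps, the false-positive rate at 100 to 150 per group runs from little above nominal (6% to 7% for 4% v 3%) to 43% to 59% (25% v 15%). These figures rest on assumed rates, a two-sided 5% test and independent patients.

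The documents do not support the stronger conclusion that participating practices already screen more, or that a positive result would be spurious. They show only that the plan could not tell. Because the remedy is cheap, the change should be made.

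**What to change.** 1. From the same EMR, rebuild the potentially eligible cohort at participating and non-participating practices as of an index date before launch. Apply the same criteria, including no lung CT in the year before that date, and define the index date in the same way in both groups.
2. Measure LDCT completion over the following 60 days. The window must end before launch.
3. Where possible, use these rates to choose control practices with similar baseline LDCT completion.
4. Report the pre-period difference beside the Aim 1 result.
5. Prespecify a difference-in-differences sensitivity analysis: (DCP group − participating practices before launch) − (matched controls − non-participating practices before launch). State its assumption that the gap between practice types would otherwise have stayed constant.
6. Do not rely on regression adjustment for the practice baseline rate if there are few practices: it would be nearly collinear with group. The number of practices is not stated.

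The cost is a modest extra EMR query, a short addition to the statistical section and lower precision in the sensitivity estimate. The pre-period cohort is all listed patients, whereas the DCP group is consenting enrollees (150 expected from 2000 listed). The fix therefore addresses practice-level confounding only. Patient self-selection into the DCP remains and should be stated as a limitation.
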